## REVISION HISTORY

### Revisions per Amendment 03

Date: 24 Sep 2018

Change	Rationale	Affected Protocol Sections
The term “systemic” was added to Treatment of Physician’s choice (TPC) to specify and add clarity that only systemic treatment following lenvatinib treatment will be considered as subsequent TPC.	The update was made to highlight that only “systemic” treatment will be considered as subsequent TPC for the study and that locoregional procedures will not be considered as subsequent TPC.	Synopsis: Objectives, Study Design, Study Treatments, Subsequent Treatment of Physician Choice (TPC), Endpoints Section 7.1 Section 8.1 Section 8.2 Section 9.1 Section 9.1.2.2 Section 9.1.2.3 Section 9.2 Section 9.4.1.2 Section 9.7.1.1.1 Section 9.7.1.1.2
It was clarified that any locoregional therapies (ie, chemoembolization / radioembolization, etc.) will not be considered as second line treatment following lenvatinib.	The update was made to highlight that locoregional procedures will not be considered as subsequent TPC for the study.	Synopsis: Study Design Section 9.1.2.2 Section 9.4.1.2
Remove ambiguous wording in the protocol to make clear that the TPC period is not optional. The continuation to second line treatment is expected as long as commercially available systemic second line treatment is deemed by the physician to be clinically appropriate. The choice of which second line treatment is used is at the discretion of the physician.	The change was made to highlight that the subsequent TPC period following lenvatinib is not optional, and that if eligible, subjects should receive systemic TPC as second line treatment.	Synopsis: Subsequent Treatment of Physician Choice (TPC) Section 9.1 Section 9.4.1.2
Study rationale was updated to further clarify the purpose of the study with focus on addressing the unmet medical need for data for safety and efficacy on the subsequent sequential therapies after 1st line therapy with lenvatinib in uHCC patients,	The study rationale was updated to provide additional clarity for the purpose of the study.	Section 7.1


US package insert was replaced with the lenvatinib Global Investigator's Brochure (GIB) as a reference for the dose adjustments and drug-drug interactions for lenvatinib.
	
The US package insert was replaced with the GIB as the source of reference for the drug-drug interaction section since the GIB is provided to all investigators for reference and includes all information presented in the section on drug-drug interactions in the protocol. Also, the GIB would be an appropriate reference for sites in Canada.
	
Section 9.4.7.1

Updated information for lenvatinib interactions with other co-administered drugs which are CYP3A4/Pgp substrates: “In a formal drug-drug interaction study, lenvatinib did not alter plasma concentrations of midazolam (a sensitive CYP3A and Pgp substrate). Thus, lenvatinib is not expected to alter the metabolism of other co administered drugs which are CYP3A4/Pgp substrates”.
	
The information was updated to present the latest information on lenvatinib drug-drug interactions.
	
Section 9.4.7.1

Clarified that echocardiograms (ECHO) should be performed locally in accordance with the institution's standard practice. The requirement to submit ECHO and MUGA scans to the central laboratory for analysis and archiving was deleted.
	
Reference to central laboratory in previous protocol versions was an error, and was removed to reflect that the study does not require a central laboratory for these assessments (ECHO and MUGA scans).
	
Section 9.5.1.5.7

Clarified that a gastroenterological endoscopy at screening is necessary only if more than 3 months have passed since the previous assessment. Gastroenterological endoscopy must have been performed within 3 months prior to receiving first dose of the study treatment.
	
Added to emphasize the requirement of a gastroenterological endoscopy within 3 months prior to receiving the first dose of the study treatment.
	
Section 9.5.2.1 (Table 3 – Footnote e)

## Revisions per Amendment 02

Date: 15 Mar 2018

Change	Rationale	Affected Protocol Sections
Secondary objective was updated as follows: 

• Evaluation of objective response rate (ORR) and clinical benefit rate (CBR) in both the first-line lenvatinib treatment period and the subsequent TPC period was deleted.

• Progression-free survival (PFS) and time to progression (TTP) will be evaluated for the subsequent treatment of physician choice (TPC) starting from the first dose of first-line lenvatinib treatment.

	The changes to the secondary objective were made because there is no meaningful way to summarize the ORR for the duration of the study. Clarify that PFS and TTP will be evaluated for the subsequent treatment of physician choice (TPC) starting from the first dose of first-line lenvatinib treatment	Synopsis: Secondary Objectives Section 7.1 Section 8.2
Secondary endpoints were updated in line with changes in the secondary objective as follows: 

• Progression-free survival (PFS), defined as the time from the date of first dose of first-line lenvatinib treatment to the date of first documentation of disease progression, or date of death during the subsequent TPC, whichever occurs first.

• Time to progression (TTP), defined as the time from the date of first dose of first-line lenvatinib treatment to the date of first documentation of disease progression during subsequent TPC.

• Evaluation of ORR and CBR was deleted.

	Secondary endpoints were updated to align with the changes in the secondary objective.	Synopsis: Secondary Endpoints Section 9.7.1.1.2
Efficacy analysis: 

• Evaluation of PFS and TTP for both treatment periods was deleted since PFS and TTP will be evaluated for the subsequent TPC period following first-line lenvatinib treatment.

• Evaluation of ORR was deleted.

	Efficacy analyses were updated based on changes in secondary objectives and secondary endpoints.	Synopsis: Efficacy Analyses Section 9.7.1.6

Change	Rationale	Affected Protocol Sections
Sample size rationale was updated.	The rationale was updated to be consistent with the primary objective.	Synopsis: Sample Size Rationale Section 9.7.2
Study rationale was updated for further clarity. Data presented formerly in Introduction section regarding survival follow-up period in Study E7080-G000-304 was moved to Study Rationale section to provide additional clarity for rationale of the study.	To provide more clarity for the rationale of the study.	Section 7 Section 7.1
Study design text was updated to clarify that the study will evaluate safety and efficacy of subsequent TPC (commercially available) following first-line lenvatinib treatment.	Text was updated to align with the primary objective.	Synopsis: Study Design Section 7.1 Section 9.1 Section 9.2
Criterion for non-hepatic target lesion in the inclusion criteria was updated to delete specifications for porta hepatis lymph node.	To avoid confusion for the inclusion criteria for non-hepatic lesions.	Synopsis: Inclusion criteria Section 9.3.1 Appendix 2
Information on treatment included in TPC was added in the section for study treatments.	To provide TPC information in synopsis.	Synopsis: Study Treatments
For the TPC, the following sentence was deleted 'Once the dose has been reduced, it cannot be increased at a later date'.	To emphasize that decisions on dosing reduction/interruptions will be based on the prescribing information for the TPCs.	Synopsis: Subsequent Treatment of Physician Choice (TPC) - Dose Reduction and Interruption Section 9.4.1.2
Definition of concomitant medications was updated to include medications up to 28 days after last dose of TPC if subject does not stay in the TPC period for the 8 weeks of safety monitoring.	To align data collection.	Section 9.4.7 Section 9.5.2.1 (Table 3) Section 9.7.1.5
Appendix 2 for mRECIST was updated to include additional examples for non-target lesions.	To provide additional examples for selection of non-target lesions.	Appendix 2
Table in Appendix 8 for CYP3A4 substrates, inhibitors, and inducers was deleted and it was clarified that the http://medicine.iupui.edu/clinpharm/ddis/ website should be referred to for most updated information on CYP3A4 substrates, inhibitors, and inducers.	To refer to most updated information on CYP3A4 substrates, inhibitors, and inducers.	Appendix 8

## **Revisions per Amendment 01**

**Date: 26 Jan 2018**

Change	Rationale	Affected Protocol Sections
Title of the protocol was reworded to “A Single-Arm, Multicenter, Phase 2 Trial to Evaluate Safety and Efficacy of Treatment of Physician Choice (TPC) Following First-Line Treatment of Lenvatinib in Subjects With Unresectable Hepatocellular Carcinoma (uHCC).”	The title of the protocol was reworded to add clarity and to align with the updated text for the primary objective and the primary endpoint.	Title page Synopsis: Study Protocol Title
Primary objective and primary endpoint were reworded as assessment of safety and tolerability of subsequent TPC following the first-line lenvatinib treatment in uHCC subjects.	Updated to add clarity.	

• Synopsis: Primary Objective, Primary Endpoint

• Section 8.1

• Section 9.7.1.1.1

The schedule for safety data collection during TPC (ie, Treatment Period 2 [TP2]) was specified with updates made in Table 3.  It was also specified that AEs will be reported until 28 days after the last dose of lenvatinib treatment if subjects do not enter TPC period, or for 8 weeks after the start of TPC period. SAE information should be collected for 8 weeks after the start of the TPC, or for at least 28 days after the last dose of lenvatinib/TPC if subjects do not continue into the TPC period or do not stay in the TPC period for the 8 weeks of safety monitoring (Table 3, footnote “z”, Section 9.5.1.5.1, and Section 9.5.4.1).  The following footnote (footnote “aa”) was added in Table 3 to clarify assessments after week 16: After week 16, only tumor assessment and TPC dose information will be collected until the end of TPC (disease progression, development of unacceptable toxicity, subject request, withdrawal of consent, or study termination by the sponsor).	The schedule for data collection during TPC was specified to allow systematic collection of safety data during TPC period following 1st line lenvatinib treatment of uHCC.	

• Synopsis: Study Design, Safety Assessments

• Section 9.1.2.2

• Section 9.5.1.5

• Section 9.5.2.1 (Table 3)


For TP2, it was clarified that subjects starting subsequent TPC <math>\geq 8</math> weeks after lenvatinib off-treatment visit may be considered after discussion with sponsor.
	
To add clarity about the TPC period duration.
	
 
• Synopsis: Study Design
 
• Section 9.1.2.2
 

For subsequent TPC definition, it was clarified that the first treatment of a single agent or combination of multiple drugs after lenvatinib treatment will be considered as the subsequent TPC.
 
Chemoembolization procedures will not be considered as a second line treatment following lenvatinib. If commercially available TPC is not used as the subsequent treatment following lenvatinib treatment, subjects will be followed in the survival follow up period.
	
To provide clarity of definition of TPC.
 
Added in 1 to provide clarity on chemoembolization procedures.
	
 
• Section 9.4.1.2
 
• Section 9.1.2.2
 

For the duration of TPC, it was clarified that subjects will continue to receive TPC treatment until disease progression, development of unacceptable toxicity, subject request, withdrawal of consent, or study termination by the sponsor.
		
 
• Synopsis: Duration of Treatment
 
• Section 9.4.1.2
 

For concomitant medications, it was clarified that concomitant medications will be recorded until 28 days after last dose of lenvatinib treatment if subjects do not enter TPC period, or for 8 weeks after the start of TPC period. All anticancer therapy will be recorded until time of death or termination of survival follow-up.
	
Updated to adjust the assessment schedule.
	
 
• Section 9.4.7
 
• Section 9.7.1.5
 
• Section 9.5.2.1 (Table 3)
 

Assessment of special chemistries was added at Baseline and C1D15. Pregnancy test at the Treatment Period 1 off -treatment visit was deleted.
 
Also, it was clarified that NYHA cardiac disease classification should only be performed at Screening if needed.
	
Updated to adjust the assessment schedule.
	
 
• Section 9.5.2.1 (Table 3)
 


For the pharmacodynamic blood (serum/plasma) biomarkers and pharmacogenetic biomarkers assessments, it was clarified that samples will be collected at week 8 and week 16 (<math>\pm 1</math> week), and that subjects entering the subsequent TPC period should have TPC baseline sample collected unless the lenvatinib Off-Treatment visit in the lenvatinib treatment period is <math>\leq 28</math> days before the subsequent treatment starts, in which case those samples may be used as the TPC period baseline.
	
This was added for clarity on biomarker data collection during TPC period.
	
 
• Synopsis: Pharmacodynamic Blood Biomarkers, Pharmacogenetic Biomarker Assessments.
 
• Section 9.5.1.4.2
 
• Section 9.5.2.1 (Table 3)
 

Blood (whole blood) sample collection for potential genetic analysis from all enrolled subjects was added to evaluate whether genetic variation within a clinical study population correlates with response to the study treatment. The following was additionally added: Biomarker correlative analyses may be performed to explore blood or tumor biomarkers that may be useful to predict subject's response in a retrospective manner. The results of these studies are to gain further insight into the clinical mechanism of action for study drug but not foreseen to result in commercially valuable products.
 
This study will collect biomarker samples in all enrolled subjects who have consented for participation of the biomarker assessments. Participation of any future exploratory research of left over material will be optional.
	
This was added to allow potential genetic analysis from all enrolled subjects, to evaluate whether genetic variation within a clinical study population correlates with response to the study treatment.
	
 
• Synopsis: Pharmacogenetic Biomarker Assessments
 
• Section 9.5.1.4.2
 
• Section 9.5.2.1 (Table 3)
 


It was specified that in TPC period, PRO-CTCAE questionnaires will be collected 2 weeks for the first 4 weeks, and then at week 8, and week 16 (<math>\pm 1</math> week). A TPC baseline assessment should be performed unless the lenvatinib Off-Treatment visit is completed within 7 days prior to the first TPC treatment.
	
Updated to adjust the assessment schedule.
	
 
• Synopsis: Other assessments
 
• Section 9.5.1.6
 
• Section 9.5.2.1 (Table 3)
 

The analysis of extent of exposure was updated to include summarization of percentage of subjects that receive TPC, average dose intensity and relative dose intensity of lenvatinib treatment and TPC, and feasibility rate.	To obtain comprehensive information about the extent of exposure.	

• Section 9.7.1.8.1

---	---	---

## 2 CLINICAL PROTOCOL SYNOPSIS

Compound No.: E7080
Name of Active Ingredient: Lenvatinib
Study Protocol Title A Single-Arm, Multicenter, Phase 2 Trial to Evaluate Safety and Efficacy of Treatment of Physician Choice (TPC) Following First-Line Treatment of Lenvatinib in Subjects With Unresectable Hepatocellular Carcinoma (uHCC)
Investigators United States (US), Canada
Sites Approximately 20 to 25 sites
Study Period and Phase of Development Approximately 30 months from first subject enrolled to end of last subject in TPC. Phase 2
Objectives Primary Objective 

• To assess the safety and tolerability of subsequent systemic TPC following first-line lenvatinib treatment in uHCC subjects.

 Secondary Objectives 

• To evaluate overall survival (OS) in uHCC subjects treated with lenvatinib as the first-line treatment followed by systemic TPC.

• To evaluate progression-free survival (PFS) and time to progression (TTP) of subsequent systemic TPC starting from the first dose of first-line lenvatinib treatment using modified Response Evaluation Criteria in Solid Tumors (mRECIST).

• To evaluate OS by subgroups of systemic TPC.

 Exploratory Objectives 

• To measure the patient perceived burden by Patient-Reported Outcomes version of the Common Terminology Criteria for Adverse Events (PRO-CTCAE) in the subsequent TPC period.

• To explore biomarkers based on availability of serum and tissue samples.

Study Design This study is a single-arm, open-label, multicenter, phase 2 trial to evaluate safety and efficacy of subsequent systemic TPC (commercially available) following first-line lenvatinib treatment in subjects with uHCC. The study will consist of a Pretreatment Phase and a Treatment Phase. The pretreatment phase will last up to 21 days and will include the Screening Period to obtain informed consent and establish protocol eligibility, and the Baseline Period to confirm protocol eligibility and disease characteristics. The Treatment Phase consists of 2 treatment periods (Lenvatinib Treatment Period [Treatment Period 1] and the Subsequent TPC Treatment Period [Treatment Period 2]) and a Follow-Up Period. The Lenvatinib Treatment Period (Treatment Period 1) for each subject will begin at the time of the first dose of lenvatinib study treatment and will consist of lenvatinib treatment on 28-day cycles until

completion of the lenvatinib Off-Treatment Visit that will occur within 30 days after the final administration of lenvatinib.

Lenvatinib treatment cycles will be counted continuously regardless of dose interruptions. Subjects will undergo safety and efficacy assessments as defined in the Schedule of Procedures/Assessments. Subjects will continue to receive study treatment until disease progression, development of unacceptable toxicity, subject request, withdrawal of consent, or study termination by the sponsor.

Subjects will be permitted to continue lenvatinib treatment beyond mRECIST defined disease progression as long as the treating investigator considers that there is clinical benefit and, the subject is tolerating study treatment. The assessment of clinical benefit should take into account whether the subject is clinically deteriorating and unlikely to receive further benefit from continued treatment. All decisions to continue treatment beyond initial progression must be discussed with the Eisai Medical Monitor. Subjects will discontinue study treatment upon evidence of further progression and/or loss of clinical benefit, as judged by the investigator.

The Subsequent Treatment Period (TPC period, Treatment Period 2) will begin upon the completion of lenvatinib Off-Treatment Visit in first-line treatment of lenvatinib. Subjects will be treated by commercially available systemic TPC for uHCC. Locoregional therapies (ie, chemoembolization/radioembolization, etc.) will not be considered as a second line treatment following lenvatinib. If the investigator deems a subject inappropriate for commercially available systemic TPC as the subsequent treatment following lenvatinib, subjects will be followed in the survival Follow-Up period. All treatment following lenvatinib will be captured in the case report form. Data will be collected from the start of TPC, then at intervals as indicated in Schedule of Procedures/Assessments ([Table 3](#)).

Subjects starting subsequent systemic TPC  $\geq 8$  weeks after lenvatinib off-treatment visit may be considered after discussion with sponsor.

The Follow-Up Period will begin immediately after the final visit in the subsequent treatment period (Treatment Period 2). Subjects will be followed every 12 weeks for survival and will continue as long as the study subject is alive, unless the subject withdraws consent. If the investigator deems a subject inappropriate for commercially available subsequent systemic TPC, the subject will be followed for survival every 12 weeks after the lenvatinib Off-Treatment Visit in the lenvatinib treatment period (Treatment Period 1). Subjects' survival status and all additional anticancer treatments received will be recorded.

The sponsor may decide to terminate survival follow-up of subjects after the completion of the primary analysis or when all subjects have discontinued study treatment.

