### **Duration of Treatment**

#### **Lenvatinib treatment (Treatment Period 1)**

Lenvatinib treatment will continue until disease progression, development of unacceptable toxicity, subject requests to discontinue, withdrawal of consent, or sponsor termination of the study. The duration of lenvatinib treatment for each subject is estimated to be 6 to 8 months.

Once disease progression occurs, lenvatinib treatment may not be restarted and subject should be considered for subsequent TPC.

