### **Secondary Endpoints**

- Overall survival (OS), measured from the date of first dose of study treatment until date of death from any cause. Subjects who are lost to follow-up will be censored at the last date the subject was known to be alive, and subjects who remain alive will be censored at the time of data cutoff.
- Progression-free survival (PFS), defined as the time from the date of first dose of first-line lenvatinib treatment to the date of first documentation of disease progression, or date of death, during the subsequent systemic TPC, whichever occurs first.
- Time to progression (TTP), defined as the time from the date of first dose of first-line lenvatinib treatment to the date of first documentation of disease progression during the subsequent systemic TPC.

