##### 9.5.1.3.1 TUMOR ASSESSMENTS

Tumor assessments will be performed during the Screening/Baseline phase (standard of care scans performed up to 28 days before the first dose of study treatment are acceptable) and then every 8 weeks ( $\pm 1$  week), or sooner if clinically indicated, during the Lenvatinib Treatment Period until disease progression ([Table 3](#)).

Subjects who discontinue lenvatinib treatment without disease progression should have tumor assessments performed (within 1 week of the lenvatinib Off-Treatment Visit) if more than 4 weeks have passed since the previous assessment and if the subject will not continue with follow-up scans.

Subjects entering the subsequent TPC period should have TPC baseline tumor assessments performed unless the last tumor assessment performed in the Lenvatinib Treatment Period is less than 28 days before the subsequent treatment starts, in which case those scans may be used as the TPC period baseline. A new tumor assessment baseline (selection of target and non-target lesions and calculation of a new baseline sum of diameters (SOD) must be established before beginning TPC. Subjects will continue tumor assessments during the subsequent TPC period every 8 weeks ( $\pm 1$  week), or until disease progression, subject death, withdrawal or loss to follow-up.

Tumor assessments will utilize mRECIST based on Lencioni and Llovet ([Appendix 2, Lencioni and Llovet, 2010](#)). Copies of all tumor imaging scans will be sent to an imaging core laboratory designated by the sponsor for potential future review. All subjects are required to undergo chest, abdomen, and pelvis imaging at baseline and all follow-up time points. Contrast-enhanced CT of the chest and contrast-enhanced CT or MRI of the abdomen, pelvis, and any other areas of disease, as clinically indicated, will be acquired at Screening and at all imaging time points. Liver CT or MRI must be performed using triphasic scanning technique optimized to capture precontrast, arterial and portal venous phase.

Screening tumor assessments using triphasic liver CT/MRI (optimized for pre-contrast, arterial phase, and portal venous phase), contrast-enhanced CT of the chest, and contrast-enhanced CT or MRI of abdomen, pelvis, and other areas of known disease plus suspected disease should be performed within 28 days prior to treatment.

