##### 9.7.1.1.2 SECONDARY ENDPOINTS

- Overall survival (OS), measured from the date of first dose of study treatment until date of death from any cause. Subjects who are lost to follow-up will be censored at the last date the subject was known to be alive, and subjects who remain alive will be censored at the time of data cutoff.
- Progression-free survival (PFS), defined as the time from the date of first dose of first-line lenvatinib treatment to the date of first documentation of disease progression, or date of death, during the subsequent systemic TPC, whichever occurs first.
- Time to progression (TTP), defined as the time from the date of first dose of first-line lenvatinib treatment to the date of first documentation of disease progression during subsequent systemic TPC.

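### PFS and TTP of TPC are timed from the first lenvatinib dose, so they describe the whole treatment sequence and do not isolate TPC

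*Combined protocol and SAP*

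**What the plan says.** The Synopsis (Study Design) states the aim: "to evaluate safety and efficacy of subsequent systemic TPC (commercially available) following first-line lenvatinib treatment in subjects with uHCC". The matching secondary objective in the Synopsis, repeated in substance in Section 8.2, is "To evaluate progression-free survival (PFS) and time to progression (TTP) of subsequent systemic TPC starting from the first dose of first-line lenvatinib treatment".

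Section 9.7.1.1.2 and the Synopsis give the same definitions. PFS is "the time from the date of first dose of first-line lenvatinib treatment to the date of first documentation of disease progression, or date of death", restricted to the TPC period. TTP has the same origin and ends at first progression during TPC. OS also starts at the first dose of study treatment.

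Four other provisions bear on the point:
- Synopsis, Duration of Treatment: "The duration of lenvatinib treatment for each subject is estimated to be 6 to 8 months". Progression is one of the listed reasons to stop.
- Section 9.1.2.1: lenvatinib may continue beyond mRECIST progression if the investigator sees clinical benefit. The Off-Treatment Visit falls within 30 days of the last dose.
- Section 9.1.2.2: TPC follows that visit. A start 8 weeks or more after it needs discussion with the sponsor.
- Section 9.5.1.3.1: a new selection of lesions and a new baseline sum of diameters "must be established before beginning TPC". Scans then follow every 8 weeks.

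**The concern.** The event belongs to TPC but the clock belongs to lenvatinib. Progression on TPC is judged against a TPC baseline, yet its time is counted from a date many months before that baseline existed. Three things follow, and limiting the analysis to subjects who start TPC removes none of them.

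- Lenvatinib duration and the wait for TPC enter the result in full, although neither says anything about TPC.
- The measure is not progression-free time. A subject who progressed on lenvatinib at month 6 and on TPC at month 10 is recorded as 10 months progression-free.
- One label covers two events. In that subject the endpoint is a second progression. In a subject who left lenvatinib for toxicity it is a first progression.

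At stake is whether the report can say anything tumor-based about TPC itself. As defined, a change in the reported median could come from TPC, from lenvatinib or from the gap, and the endpoint cannot tell them apart.

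**Working it through.** **What the text fixes.** The PFS sentence could be read two ways, because the phrase about the TPC period follows the mention of death. The TTP definition settles it, since it ties progression itself to the TPC period. For a TPC recipient:

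S = L + G + T

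where L is time on lenvatinib, G is the gap from last lenvatinib dose to first TPC dose, and T is time from first TPC dose to the event. By definition no event can occur during L or G.

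**Inputs.**
- L: 6 to 8 months (Synopsis).
- G: up to 30 days plus 8 weeks before the sponsor-discussion rule applies, that is (30 + 56)/30.44 = 2.8 months (Sections 9.1.2.1 and 9.1.2.2).
- T: not given in the documents; assumed.

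**The plan's own figure.** PFS and TTP have no precision or power figure. The only design calculation is Table 4 (Grade 3 or higher TEAE rate), which reproduces: 1.96 × sqrt(0.75 × 0.25/n) gives 8.49% at n = 100 and 12.00% at n = 50, against the stated 8.5% and 12%. It is unaffected by this point.

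**Fixed-time shares.** The lenvatinib share is L/(L + G + T). With G = 0:
- T = 3 months: 6/9 = 67% to 8/11 = 73%
- T = 6 months: 6/12 = 50% to 8/14 = 57%
- T = 10 months: 6/16 = 38% to 8/18 = 44%

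Lenvatinib exceeds half of S only when G + T is shorter than L.

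**Random times.** Assume L, G and T are independent, L exponential with median 6, 7 or 8 months, G uniform on 0.25 to 2.8 months, and T exponential with median 3, 4.5 or 6 months. An exponential mean is median/ln 2 and its variance is the mean squared. G has mean 1.525 and variance 2.55²/12 = 0.54.

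Example, L median 6 and T median 3: means are 8.66 and 4.33. TPC's variance share is 4.33²/(8.66² + 0.54 + 4.33²) = 20%. Lenvatinib's share of mean time is 8.66/(8.66 + 1.525 + 4.33) = 60%.

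| TPC median (months) | Variance explained by TPC | Lenvatinib share of mean time |
|---|---|---|
| 3 | 12-20% | 60-66% |
| 4.5 | 24-36% | 52-59% |
| 6 | 36-50% | 46-53% |

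Ranges run over lenvatinib medians of 6 to 8 months.

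**Effect on the reported median (simulation, same assumptions).**
- Lenvatinib median 7, TPC median 3 to 6 months: 13.2 to 17.3 months. 17.3/13.2 = 1.31, so a true doubling shows as about +30%.
- TPC median fixed at 3, lenvatinib median 6 to 8 months: 12.2 to about 14.2 months.
- Lenvatinib median fixed at 6, TPC median 3 to 4.5 months: 12.2 to 14.2 months.

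A change in lenvatinib duration within the protocol's own range thus looks the same as a 50% longer TPC PFS.

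**Sensitivity.** If 6 to 8 months is read as a mean, TPC's variance share is 22-34% at a TPC median of 3 months and 54-67% at 6 months.

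**The case against.** The origin is deliberate and disclosed. Amendment 02 chose it, the objective states it, and the definitions follow it consistently. The rationale in Section 7.1 concerns sequential therapy after lenvatinib, so a sequence-level endpoint is defensible. This stands: the passages do not contradict each other. It does not answer the point, because a sequence measure is presented as PFS and TTP of TPC and nothing else measures TPC.

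Three stronger readings are tempting, and the documents do not support them.
- *The endpoint mostly measures time on lenvatinib.* The documents give no PFS on TPC. At an assumed TPC median of 6 months, lenvatinib is about half of mean time.
- *The endpoint cannot show TPC efficacy.* It responds to TPC, but in diluted form. Re-timing would not establish efficacy either: the trial is single-arm, TPC pools any commercially available systemic product, and there is no comparator.
- *Response on TPC should be restored.* Amendment 02's stated reason, "there is no meaningful way to summarize the ORR for the duration of the study", may seem not to reach the TPC period. But the deletion of ORR and CBR expressly covered both periods, and response is not needed to correct the time origin.

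It is also fair that the planned PFS and TTP analyses are descriptive Kaplan-Meier summaries, that the TPC subgroup objective concerns OS only, and that the primary endpoint is safety. These limit the consequences. Finally, Section 9.7 defers analysis details to a separate SAP, so the absence of a TPC-origin endpoint is established for the protocol text only.

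**Conclusion.** The mismatch between objective and endpoint is real and rests on the protocol's wording alone. PFS and TTP of TPC include all lenvatinib time and the gap as event-free time, include any time after progression on lenvatinib, and mix first and second progressions. They describe the sequence and do not isolate TPC, and no efficacy endpoint in the protocol is timed from TPC start.

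The size is conditional. The variance shares and the roughly 30% rise for a true doubling assume independent exponential times, 6 to 8 months read as a median, and a uniform gap. The dilution is heavy if PFS on TPC is near 3 months and moderate near 6. The mismatch remains at any value.

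It concerns secondary endpoints, the data needed are already collected, and the correction is cheap, so it should be made but does not threaten the primary analysis. Which subjects are analysed, and how those who never start TPC are handled, is a separate question.

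**What to change.** In the Synopsis and Sections 8.2 and 9.7.1.1.2, define PFS and TTP of TPC from the date of the first TPC dose to first progression against the TPC baseline scan (for PFS, also to death), in subjects who received at least one dose of TPC. Carry the same definitions into the SAP.

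Keep the lenvatinib-origin measure only under a sequence label, for example PFS2 or time to progression on next-line therapy.

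The cost is wording plus one further set of Kaplan-Meier outputs. Post-lenvatinib treatment and TPC dosing, the TPC baseline scan and the 8-weekly TPC scans are already collected. The downside is precision: the analysed number falls from 100 to the TPC recipients (more than 50 by the planning assumption), so confidence intervals are wider than for 100 subjects.
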